Official Title:	Impact of Online Ordering on Low-Income Adults' Food Security in Online Food Pantry Settings
NCT Number:	NCT05752721
Study Number:	22-01523
Document Type:	Study Protocol and Statistical Analysis Plan
Date of the Document:	
September 14, 2023

STUDY PROTOCOL

Impact of Online Ordering on Low-Income Adults' Food Security in Online Food Pantry Settings

NYULH Study Number

s22-01523

Principal Investigator

[name]

Protocol Version

September 7, 2023

Study Personnel

Principal Investigator

[name]
NYU Grossman School of Medicine
Department of Population Health
[name]
[name]
Email: [contact]
[contact]

Research Coordinator

[name]
NYU Grossman School of Medicine
Department of Population Health
[name]
[name]
Email: [contact]
[contact]

Synopsis

Study Description

The specific aims of this proposal are to 1) ascertain whether the transition to online ordering at a choice-based food pantry network in New York City influences food security status among 386 food pantry clients and 2) determine whether there are differences in outcome by age group (18-61 vs. ≥ 62 years).

To accomplish Aim 1, study team members will conduct a natural experiment with two conditions in food pantry sites within the Met Council Kosher Food Pantry Network. To accomplish Aim 2, we will test for potential interaction effects at the individual-level by adding an interaction term for age group.

Overall, the research study will occur over 18 months (see timeline below). Year 1 will involve survey design and data collection. Year 2 will involve data analysis and development of dissemination materials.

Table 1. Timeline	Year 1 of grant												Year 2 of grant					
	1	2	3	4	5	6	7	8	9	10	11	12	13	14	15	16	17	18
Design of survey, training RA, and IRB approval	X	X	X															
Data collection				X	X	X	pause	Online ordering transition	pause	X	X	X						
Data analysis													X	X	X	X		
Write and disseminate results																	X	X

Objectives

Our primary objectives are to determine whether the transition to online ordering at a choice-based food pantry network influences food security status among low-income adults and determining whether there are differences in impact by age group.

Endpoints

The endpoint for Aim 1 for the intervention arm is the successful completion of the follow-up period, including food and nutrition security status, total fruits and vegetables selected per visit, total energy intake, intake of key food groups, and time to obtain food from food pantry per visit.

The endpoint for Aim 2 is the completion of data analysis.

Study Population

The study population for Aim 1 is a sample of low-income adults aged ≥ 18 years..

Accrual Ceiling

We require a total sample size of 193 participants per condition for Aim 1 (total n=386).

Aim 2 will not involve participant enrollment.

Phase

Not applicable.

Description of Sites/Facilities Enrolling Participants

We propose to recruit participants from food pantry clients at food pantry sites within the Met Council Kosher Food Pantry Network, a network that contains 65 pantry partners and over 200 community partners in NYC. Met Council procures and distributes kosher food to their network of kosher food pantries and provides ongoing support with reporting, pantry set up and maintenance, advocacy, and programming. The Network primarily serves immigrants, seniors living on fixed incomes, the un- and underemployed and anyone else in need in immigrant-dense neighborhoods.

Study Duration

The study will last 18 months, but data collection will specifically occur in 2 time periods, including months 4-6 and 10-12 in Year 1 of the study.

Participant Duration

The total participant duration will be approximately 30-50 minutes to complete the survey and record food selections for both data collection periods.

Schedule of Activities (SoA)

During the baseline data collection period, all participants will complete a survey about their food and nutrition security, diet behaviors, and frequency of food pantry visits. To finish, the Research Assistant will record their food selections from the current food pantry visit.

During the follow-up data collection period, all participants will complete a survey about their food and nutrition security, diet behaviors, and frequency of food pantry visits. Participants in the control arm will record their food selections from their most recent food pantry visit and send them to the study team.

End of Study Definition

The end of the study is when we have disseminated our results.

1 – Statement of Compliance

1.1 Statement of Compliance

This study will be conducted in accordance with the Code of Federal Regulations on the Protection of Human Subjects (45 CFR Part 46), any other applicable US government research regulations, and institutional research policies and procedures. The Principal Investigator will assure that no deviation from, or changes to the protocol will take place without prior agreement from the sponsor and documented approval from the Institutional Review Board (IRB), except where necessary to eliminate an immediate hazard(s) to the study participants. All personnel involved in the conduct of this study have completed Human Subjects Protection Training.

2 - Introduction

2.1 Background

Compared to food secure adults, adults experiencing food insecurity have lower energy intake, lower intake of key nutrients, and poorer diet quality.¹⁻⁵ Food insecurity is also associated with poor or fair health, underweight status, and chronic health issues, such as diabetes and hypertension.²⁻¹² Malnutrition among low-income adults who use food pantries is also linked to a lack of housing, barriers to accessing health care and other social resources, unemployment, substance abuse, and domestic conflict.¹³

In NYC, 1.5 million residents are food insecure, a 36% increase from before the COVID-19 pandemic.¹⁴ Evidence from survey research suggests that food insecurity and hunger are also higher among immigrants (vs. non-immigrants) and older (vs. younger) adults in NYC, potentially due to higher rates of income inadequacy and fixed incomes, respectively.¹⁵⁻¹⁷ These disparities are likely to grow in the future given how population growth in NYC is driven by older adults, and how population growth of older adults is driven by growth in immigrant older adults.¹⁸

In the Parent Grant, we established how nutrition assistance programs, such as meal delivery programs and the Supplemental Nutrition Assistance Program (SNAP), address key barriers to healthy eating in low-income adults. Food pantries are also a key source of nutrition and healthy foods for low-income adults, especially for low-income older adults, who use food pantries as their primary source of food assistance.^{19,20} In NYC, approximately 1.4 million residents rely on food pantries for emergency food assistance each year, including one out of every five older adults.¹⁷ Previous studies show that visiting a food pantry mitigates food insecurity among food pantry clients,²¹⁻²³ and may improve diet quality among food insecure clients.^{24,25} The use of food pantries may also mitigate chronic disease risk among food pantry clients, including diabetes and heart disease.^{21,26}

However, mistrust of emergency food resources may be disproportionately higher in immigrant (vs. non-immigrant) communities,²⁷ potentially due to stigma, fear of interaction with government representatives (e.g. NYPD, ICE), and other factors.²⁸ Evidence from qualitative research, for example, suggests that the stigma of waiting in public to be served reduces utilization and satisfaction of food pantries.²⁹ This was corroborated by a recent review study noting how food pantry clients describe reasonable wait times and an “easy process” as a cornerstones of good customer service in food pantry settings.³⁰ Thus, strategies to increase food pantry use may support food security and healthy eating behaviors among low-income adults, especially those designed to mitigating the high opportunity costs of waiting in line and stigma, such as digital ordering.

In the Parent Grant, we are leveraging the rapid growth in online grocery shopping and expansion of retailers accepting SNAP benefits in online transactions. The recent shift to online ordering in some food pantries affords a similar opportunity to support food security and a healthy diet among low-income adults, which we aim to leverage in this Administrative Supplement. Online ordering is available in a small number of food pantries across the U.S., such as the Portland Open Bible Community Pantry in Portland, OR and The Open Door in Essex County, MA, largely due to increases in food insecurity and social distancing measures during the COVID-19 pandemic.^{31,32} Anecdotal evidence suggests online ordering has contributed to increased food pantry use, potentially due to reductions in wait times, reduced stigmatization, and increases in self-efficacy and self-sufficiency.³³⁻³⁷ Increases in food pantry, in

turn, may improve food pantry clients' food security status and increase fruit and vegetable intake relative to a traditional distribution model,^{38,39} especially in combination with changes to food "pricing" (e.g., assigning foods with high nutritional value fewer points than less healthy food). To our knowledge, however, there have been no evaluations of the transition to online ordering in food pantries.

2.2 Study Rationale

The successful completion of the proposed research may highlight and support the development of a novel approach to improving food security and healthy food choices in a high-need population.

2.3 Potential Risks and Benefits

2.3.1 Known Potential Risks

There is a risk of breach of confidentiality. To reduce the likelihood of a breach of confidentiality, we will store the survey responses on Qualtrics, which is password protected and encrypted. We will collect names, phone numbers, email addresses, and mailing addresses in a secure REDCap form to facilitate data collection in the follow-up period, which will be conducted virtually, and to distribute gift cards. The REDCap data will not be linked to Qualtrics survey responses. The content of the participants' responses to survey questions will pertain only to their food and nutrition security status, intake of key foods, and frequency of food pantry visits. We will not be asking for information that could place the participants at risk of criminal or civil liability or be damaging to the participants' financial standing or employability.

Participants may receive texting over mobile/cell phones and this method of communication may also result in a breach of their confidential information because text messages to mobile/cell phones are not encrypted. This method of communication will only be used with participants' agreement/consent.

Participants may become frustrated when completing the survey. It will be made clear to participants that they are free to skip any questions they do not wish to answer or stop at any time.

2.3.2 Known Potential Benefits

There are no direct benefits to subjects. This study will provide evidence to be used in evaluating the effect of food pantries' transitioning to online ordering on clients' food selection. Met Council and other food pantries will be able to reference this information when deciding whether to transition their pantries to online ordering.

3 - Objectives and Endpoints

3.1 Primary Objective

Our primary objectives are to determine whether the transition to online ordering at a choice-based food pantry network influences food security status among low-income adults and determining whether there are differences in impact by age group.

3.2 Endpoints

The endpoint for Aim 1, the intervention, is the successful completion of the follow-up period data collection, including food and nutrition security status, total fruits and vegetables selected per visit, diet behaviors, and time to obtain food from food pantry per visit.

The endpoint for Aim 2 is the completion of data analysis.

4 - Study Design

4.1 Overall Design

This research study includes two aims, though only Aim 1 involves human subjects. The duration of the study is 18 months.

In Aim 1, study team members will recruit low-income adults aged ≥ 18 years. Participants will be recruited from a food pantry that is not scheduled to transition to online ordering (control) and a food pantry that is scheduled to transition to online ordering after the baseline data collection period (intervention). Participants in both arms will complete an in-person survey. Potential participants who are not able to take the survey in-person, will be offered the option to take the survey online. To assess potential changes in fruit and vegetable intake, we will administer the Behavioral Risk Factor Surveillance System (BRFSS) 6-item brief dietary assessment tool (questions 9-14 in the survey attached in Research Navigator). A Research Assistant will record the food items they received in the relevant visit to the pantry. After the transition to online ordering at the intervention food pantry, participants will again complete the survey over the phone. The survey will be administered by a member of the study team using the Follow-Up Survey Guide. Participants in the control arm will record their food selections and send them to the study team during the phone call. Food selections for participants in the intervention arm will be accessible through the online ordering platform. The study team will then analyze the baseline and follow-up data for differences in outcomes between study conditions.

In Aim 2, we will test for potential interaction effects at the individual-level by adding an interaction term for age group (18-61 vs. ≥ 62 years).

4.2 Scientific Rationale for Study Design

The design and methods proposed will achieve robust and unbiased results because random assignment to an intervention group or control group in the context of a natural experiment minimizes bias.

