5.4 Lifestyle Considerations

Participants in the intervention arm will have to transition with their food pantry to online ordering after the baseline data collection period regardless of their participation in this research study. The change will be brought on “naturally” by the food pantry (not the NYULH researchers or specifically as part of this research study). There will be no other restrictions during any other parts of the study pertaining to lifestyle and/or diet.

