5.5 Strategies for Recruitment and Retention

For Aim 1, we will choose the food pantry recruiting sites with help from Met Council Kosher Food Pantry Network. We will aim to select a control site that is similar to the intervention site based on food pantry characteristics (e.g., number of food pantry clients per week, primary language(s) spoken) and community-level characteristics (e.g., neighborhood poverty level).

IRB-approved NYULH study personnel will recruit participants in person at two Met Council food pantries and will obtain permission from the food pantries prior to in-person recruitment at their

facilities. We will have support from food pantry staff members in introducing the NYULH study to potential participants. The study personnel will be on-site at the food pantry to introduce the study to food pantry clients and answer questions. Food pantry staff will also be available to direct food pantry clients to the study personnel. The study team will provide the food pantry with a recruitment flyer to post and/or pass out informing clients of the study and directing them to scan a QR code for the consent form with more information about the study and access to the study team's contact information. After scanning the QR code, clients will first see a short paragraph ("Pre-Consent QR Code Copy") listing the eligibility requirements and explaining what the consent is, in addition to a note that they do not need to sign the form at that moment. After the short paragraph, they will be able to scroll down to view the consent.

We will collect names, phone numbers, email addresses, and mailing addresses from participants in a secure REDCap form to facilitate the follow-up data collection, which will be conducted virtually, and to distribute gift cards.

Screen failures include those who do not meet all of our inclusion criteria. Potential participants will be asked to answer one pre-screening question about their age to determine their eligibility. If they do not meet our inclusion criteria, these participants will be told by the Research Assistant, "Thank you for your time, but unfortunately, you are not eligible for this study." We will immediately discard information from screen failures and from individuals that do not provide consent to take part in this study. Re-screening is not applicable.

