8.1 Statistical Hypotheses

In Aim 1, we will test the working hypotheses that 1) food security will improve (i.e. food security score will decrease) among participants visiting a food pantry that transition to online ordering in the follow-up period, but not among those in the control arm, and 2) participants visiting a food pantry that transitions to online ordering will also select more fruits and vegetables per visit, have higher fruit and vegetable intake, and spend less time accessing food pantries in the follow-up (vs. baseline) period compared to those in the control arm.

For Aim 2, we hypothesize that improvements in food security due to online ordering will be larger for younger adults.

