8.2 Sample Size Considerations

To calculate our sample size, we used estimates from a similar study that found that a food bank-delivered intervention (diabetes-appropriate food packages, text-based health education, and referrals to health care) resulted in a decrease in the mean food security score from 2.8 to 2.3, or a 6.3% decrease in the percentage of participants with low or very low food security status.⁴⁰ Based on this study, we assume the standard deviation of the food security score is 1.5 and estimate that 155 participants in each condition (total n=310) will provide 90% power to detect a 0.5 difference in food security score between experimental and control conditions. To account for a potential attrition rate of 20% in the follow-up period, we plan to recruit a total sample size of 193 participants per condition (total n=386).

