8.4 Statistical Analyses

We will perform a linear regression to assess balance of demographic characteristics between conditions; because of the natural experiment design, these characteristics should be balanced. To assess differences in outcomes between study conditions, we will regress the outcome variable on indicator variables for the experimental conditions, with the control condition as the reference group; if necessary, we will also adjust for any respondent characteristics that may be unbalanced by condition. The design and methods proposed will achieve robust and unbiased results because random assignment to an intervention group or control group in the context of a natural experiment minimizes bias.

We will also test for potential interaction effects at the individual-level by adding an interaction term for age group (18-61 vs. ≥ 62 years). In the food pantry network, an average of 25% of clients served are above 61 years of age, so we will have adequate variation to assess potential interactions by age group. For assessing differences in the frequency of food pantry visits per month at the food pantry-level, we will also add an interaction term for age group, which the

food pantry network measures as child (<18 years), adult (18-61 years), and older adult (≥ 62 years).

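### The plan claims random assignment, but it compares one pantry going online with one selected control, and its primary model does not say how the baseline score is used

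*Combined protocol and SAP*

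**What the plan says.** Section 4.2 justifies the design by promising "robust and unbiased results because random assignment to an intervention group or control group in the context of a natural experiment minimizes bias". Sections 8.4 and 8.4.8 carry the same sentence.

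The operational sections describe something else:

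- **Recruitment (4.1).** "Participants will be recruited from a food pantry that is not scheduled to transition to online ordering (control"), and from a second pantry that is due to go online after baseline.
- **Who makes the change (5.4).** The pantry does, "not the NYULH researchers or specifically as part of this research study".
- **Choice of control (5.5).** "We will aim to select a control site that is similar to the intervention site", with the network's help. The same section confirms that recruitment takes place at two pantries.

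On covariates, sections 8.4, 8.4.2 and 8.4.8 check demographic characteristics by regression and state that "because of the natural experiment design, these characteristics should be balanced". Respondent characteristics found to be unbalanced are adjusted for only if that is judged necessary.

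On the primary analysis, section 8.4.2 names food security status as the outcome and regresses the outcome variable on condition indicators. It does not say whether that variable is the follow-up level or the change, and it mentions no baseline score and no period term. Other sections intend a before-after contrast. Section 4.1 says "The study team will then analyze the baseline and follow-up data for differences in outcomes between study conditions". Section 8.1 expects that "food security will improve (i.e. food security score will decrease) among participants visiting a food pantry that transition to online ordering" at follow-up but not in the control arm. Section 8.4.3 defines the secondary outcomes as changes.

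**The concern.** Three things follow from the mismatch.

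1. The causal claim has no basis in the design. With one pantry per arm, condition and pantry are the same variable.
2. Balance cannot be expected by design, so adjusting only where an imbalance appears means choosing covariates after seeing the data. The balance check names demographics and does not mention baseline food security.
3. Three models fit the text of section 8.4.2: follow-up score alone, change from baseline, and follow-up score adjusted for baseline. Under randomisation all three would estimate the same effect. Here they need not. Follow-up alone reports any stable difference between the two clienteles as an effect of online ordering. Baseline adjustment removes part of that difference, and a change model removes it all if trends are parallel.

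A separate limit applies to every model. Anything else that changes at one pantry between the periods, such as stock or opening hours, cannot be told apart from online ordering. That comes with a two-pantry design and calls for disclosure; it is not a modelling error.

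**Working it through.** **Inputs.** From section 8.2: n = 155 per arm, SD 1.5, difference 0.5. Not in the documents, so assumed: alpha of 5% (one- and two-sided both shown), baseline to follow-up correlation r = 0.3, 0.5, 0.7, and a stable gap between pantries of 0.25 or 0.1 points.

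**Step 1: the plan's own figure.** Section 8.2 states that "155 participants in each condition (total n=310) will provide 90% power to detect a 0.5 difference in food security score".

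- SE = 1.5 × √(2/155) = 0.170.
- Power by the noncentral t distribution is 90.0% at one-sided 5% and 83.3% at two-sided 5%.

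The 90% therefore reproduces as a comparison of two independent means at one-sided 5%. No baseline score enters it.

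**Step 2: false rejection under a stable gap.** Assume no true effect, and intervention clients lower (better) by 0.25 points at both periods.

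- *Follow-up only.* The bias is 0.25. The z shift is 0.25/0.170 = 1.467, which gives rejection of 31% two-sided and 43% one-sided. With a 0.1-point gap the figures are 9% and 14%.
- *Change from baseline.* The gap cancels, so rejection is about 5%. In simulation with 20,000 runs per r it was 4.7% to 5.2% two-sided. This assumes no variation between pantries over time.
- *Adjusted for baseline.* The residual bias is 0.25 × (1 − r) and the residual SD is 1.5 × √(1 − r²):

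| r | Residual bias | Rejection, two-sided 5% | Rejection, one-sided 5% |
|---|---|---|---|
| 0.3 | 0.175 | 18.9% | 28.4% |
| 0.5 | 0.125 | 13.5% | 21.2% |
| 0.7 | 0.075 | 9.4% | 15.2% |

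**Step 3: power with 155 per arm for a 0.5 difference.** The change-score SD is 1.5 × √(2(1 − r)), and the baseline-adjusted SD is as in step 2.

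| r | Change, one-sided | Change, two-sided | Adjusted, one-sided | Adjusted, two-sided |
|---|---|---|---|---|
| 0.3 | 79.7% | 69.6% | 92.3% | 86.6% |
| 0.5 | 90.0% | 83.3% | 95.9% | 92.2% |
| 0.7 | 98.4% | 96.5% | 99.3% | 98.4% |

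A change score reaches 90% only from r of about 0.50 (one-sided) or 0.59 (two-sided). At r = 0.3, 90% power would need 217 (one-sided) or 266 (two-sided) completers per arm.

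**The case against.** The plan has real strengths: a concurrent control, an aim to match sites on client volume, language and neighbourhood poverty, baseline measurement, and an adjustment rule. That rule covers any unbalanced respondent characteristic, which could be read to include the baseline score. The balance statement credits the natural experiment rather than random assignment, and section 8.4.2 contains no random-assignment sentence. These points narrow the gap without closing it. The rule stays conditional and data-driven and never names the baseline score, while sections 8.4 and 8.4.8 place the balance statement and the randomisation claim in the same paragraph.

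The 0.25 gap is also an assumption, and nothing in the documents points to that size; at 0.1 points the follow-up-only error is 9% two-sided. That stands, and the figures illustrate sensitivity rather than predict bias.

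The change model's 5% also depends on there being no pantry-by-time variation. If each pantry drifted with an assumed SD of 0.1 points, at r = 0.5 the true SE would be √(0.170² + 2 × 0.1²) = 0.221, and a nominal two-sided 5% test would reject about 13% of the time. That stands too, and it is why the limit must be disclosed.

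Finally, power does not fall below 90% under every choice. Baseline adjustment keeps at least 90% at one-sided 5% for any r from 0 up, and at two-sided 5% from r of about 0.43. The 90% may therefore survive, but only after it is recomputed for the chosen model.

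**Conclusion.** The concern holds and must be fixed. The random-assignment claim is contradicted by sections 4.1, 5.4 and 5.5, and no section describes a randomisation procedure. The primary estimate cannot be determined from section 8.4.2.

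Under the assumed stable 0.25-point gap, the admissible models give two-sided false rejection from about 5% to 31%. With the plan's 155 per arm, power for models that use the baseline score runs from 70% to 99%, depending on model, sidedness and r between 0.3 and 0.7. These ranges rest on the assumed alpha, correlation and gap. The finding about the assignment mechanism and the missing model specification rests on the text alone.

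**What to change.** 1. **Design wording.** Remove the random-assignment sentences from 4.2, 8.4 and 8.4.8 and the balance statements from 8.4, 8.4.2 and 8.4.8. Describe a non-randomised controlled before-after comparison of two pantries.
2. **Primary model.** Prespecify one model of the 0–6 score, the quantity powered in 8.2. Choose change from baseline or follow-up adjusted for baseline, with the other as a sensitivity analysis. Fix the covariates in advance, whatever the balance tests show. If a condition-by-period form is used, enter covariates as covariate-by-period terms, because with complete pairs their main effects leave the estimate unchanged.
3. **Assumption.** State it: parallel trends for the change model; for the adjusted model, equal expected follow-up scores without online ordering among clients with the same baseline score and covariates.
4. **Pairing.** Confirm that study IDs link each person's baseline and follow-up surveys. Section 9.6 describes linkage between data types without mentioning periods, and 2.3.1 and 9.4 keep contact data apart from survey responses.
5. **Power.** Restate it for the chosen model with alpha, sidedness and assumed r.
6. **Interpretation.** State that confidence intervals and p-values exclude pantry-by-time variation, which two pantries cannot estimate, and word conclusions as an association at these two sites.

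The cost is wording, one model specification, one power statement and one ID check, using baseline scores that are already collected. The price is weaker causal language and possibly lower stated power. No new sites are needed, and no new participants if the restated power is accepted.
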